## APPENDIX 2. SEQUENTIAL ORGAN FAILURE ASSESSMENT

A clinical scoring system, SOFA (Sequential Organ Failure Assessment), is used to assess a patient's mortality risk.

### Sequential Organ Failure Assessment (SOFA) Score Scale

Variable	0	1	2	3	4	Score (0-4)
PaO 2 /FiO 2 mmHg	> 400	< 400	< 300	< 200	< 100	
Platelets, $\times 10^3/\mu\text{L}$ ( $\times 10^6/\text{L}$ )	> 150 (> 150)	< 150 (< 150)	< 100 (< 100)	< 50 (< 50)	< 20 (< 20)	
Bilirubin, mg/dL ( $\mu\text{mol/L}$ )	< 1.2 (< 20)	1.2 - 1.9 (20 - 32)	2.0 - 5.9 (33 - 100)	6.0 - 11.9 (101 - 203)	> 12 (> 203)	
Hypotension	None	MABP < 70 mmHg	Dop < 5	Dop 6 - 15 or Epi < 0.1 or Norepi < 0.1	Dop > 15 or Epi > 0.1 or Norepi > 0.1	
Glasgow Coma Scale Score (see next page to calculate)	15	13 - 14	10 - 12	6 - 9	< 6	
Creatinine, mg/dL ( $\mu\text{mol/L}$ )	< 1.2 (< 106)	1.2 - 1.9 (106 - 168)	2.0 - 3.4 (169 - 300)	3.5 - 4.9 (301 - 433)	> 5 (> 434)	
					TOTAL (0 - 24):	

Dopamine [Dop], epinephrine [Epi], and norepinephrine [Norepi] doses in  $\mu\text{g}/\text{kg}/\text{min}$  (administered for at least one hour). SI units in parentheses ()

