### Rationale for GC4419 dosing plan:

- Extensive clinical experience in cancer patients supports the safety of 90 mg of GC4419 administered over 60 minutes for 35 doses (M-F, up to 7 weeks) concurrently with chemoradiotherapy.
- Cmax-related transient mild hypotension and orthostasis has been observed at the current 90 mg/60-minute infusion schedule, but this is less frequent with lower doses.
- Therefore, administering 90 mg of GC4419 IV over 180 minutes (3 hours) is expected to provide an additional margin of safety.
- The plasma half-life of GC4419 is approximately 2 hours.
- Pharmacokinetic results to date do not indicate significant plasma accumulation of GC4419 with repeated dosing.

- Results of GLP animal toxicology studies support a total daily dose of GC4419 up to 198 mg, administered for up to 14 days (compared with planned 7 days in the current study).
- Administration of a related dismutase mimetic to rats in the zymosan and *E. coli* sepsis models was performed over a period of several hours after challenge with zymosan or *E. coli*. Moreover, the persistent superoxide production is expected to be associated with the ongoing COVID-19 disease process. Accordingly, a dosing schedule that maintains extracellular concentrations of GC4419 as much as possible and feasible may be desirable.

In light of the above, subjects will receive, in a blinded fashion, either GC4419, 90 mg intravenously, or placebo, administered over 3 hours (180 minutes), repeated every 12 hours (+/- 2 hours) for 7 consecutive days.

Subjects requiring renal dialysis should not have that procedure performed at any time during GC4419/placebo infusion and until at least 2 hours after infusion. If continuous renal replacement therapy is required for >24 hours, dosing with blinded GC4419/placebo will be discontinued.

Adverse Events and Serious Adverse Events will be assessed daily during dosing of GC4419/placebo, then daily during hospitalization and weekly after hospital discharge, for a total of 30 days after the last dose of GC4419/placebo. Post-dosing AE assessment may be done on an outpatient basis for subjects who are discharged from the hospital.

Ongoing safety results will be monitored by an independent Data Monitoring Committee (DMC) that will operate under a specific DMC charter separate from this protocol document.

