Based on case reports from the current COVID-19 outbreak, three additional nonclinical findings may also be important in subsets of patients. First, based on the understanding that in the hyperinflammatory state,  $O_2^{\bullet-}$  can initiate the auto-oxidation of catecholamines, leading to self-perpetuating refractory hypotension, the MnPAM dismutase mimetics have been shown in multiple models to restore response to vasopressor therapy and maintain mean arterial blood pressure [36-38]. It is unclear how broadly refractory hypotension is an issue for critically ill COVID-19 patients, however renal failure does seem to be a substantial issue. While renal failure may be due to compromised circulation (perhaps stemming from refractory hypotension), acute kidney injury has also been linked directly to  $O_2^{\bullet-}$  and such injury is reduced by the MnPAM dismutase mimetics in models of direct injury by cisplatin and of the zymosan-induced inflammatory response [30,34]. In addition, in a randomized Phase 2 setting, post hoc analysis suggests that GC4419 reduces chronic kidney disease in cisplatin-treated patients [57]. Finally, analogous to lung injury models discussed above, in myocardial injury models, GC4403 reduced  $O_2^{\bullet-}$ , neutrophil infiltrate, lipid peroxidation and myocardial damage, while significantly improving cardiac function post-ischemia/reperfusion, transplant or hyperglycemia [58-61], suggesting that a MnPAM dismutase mimetic might also reduce cardiac myopathy seen in some

critically ill COVID-19 patients. Further, MnSOD overexpression reverses pulmonary hypertension (PAH) in the fawn-hooded rat [62]. In alignment with that MnPAM dismutase mimetics have been shown to reduce PAH in hypoxic piglet and bleomycin rat models [63-66], which could also be a beneficial activity in patients with myocardial injury. Thus, beyond treating or preventing ARDS, in critically ill COVID-19 patients may offer help with refractory hypertension, renal impairment and heart failure co-morbidities.

While it can be debated what the best animal models of ARDS or of critically ill COVID-19 patients are, the nonclinical data above argue strongly for assessing the MnPAM dismutase mimetics in this indication, as well as for protection of other organs targeted by cytokine storm.

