### 5.2. Secondary Objectives

The following secondary objectives will be assessed through a 28-day period to align with the primary objective:

- To assess the safety of avasopasem in the study population
- To evaluate the frequency of successful ventilator weaning
- To evaluate the number of days alive and intensive care-free
- To evaluate the number of days alive and ventilator-free
- To evaluate the number of days of minimum SpO2/FIO2 ratio or PaO2/FIO2 > 300
- To evaluate the number of days alive without vasopressor/catecholamine support
- To evaluate the incidence of mean arterial pressure < 65 mmHg on optimized vasopressor therapy
- To evaluate the number of days alive with a SOFA score of 6 or less
- To evaluate the percentage of subjects with an increase in mean arterial pressure of 10 mm Hg or more at the end of more than one infusion of GC4419

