### **11.5.2. Secondary Efficacy Endpoints**

- safety of avasopasem
- frequency of successful ventilator weaning
- days alive and intensive care-free
- days alive and ventilator-free
- days alive with minimum  $\text{PaO}_2/\text{FiO}_2 \geq 300\text{mmHg}$
- days alive and without vasopressor/catecholamine support
- incidence of mean arterial pressure  $< 65 \text{ mmHg}$  on optimized vasopressor therapy
- days alive with a SOFA score of 6 or less
- percentage of subjects with an increase in mean arterial pressure of 10 mm Hg or more at the end of more than one infusion of GC4419

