 Record worst value once a day assessed 8am-6pm

 <https://intensivecarenetwork.com/Calculators/Files/Apache4.html>. Record worst value in past 24 hours at baseline visit only.

 Record highest value during any 24-hour period

 Performed locally. CBC with differential and platelets; sodium, potassium, chloride, CO2, BUN, creatinine, total protein/albumin, AST/ALT, and total bilirubin. Include direct bilirubin, triglycerides, C-reactive protein, and troponin at baseline only unless clinically indicated. If baseline troponin is above ULN, the highest post-baseline value during hospitalization and the value closest to date of discharged will also be collected. Record Worst Value for Any Day When Multiple Labs are Drawn.

 Administer 90 mg IV over 180 minutes, Q 12 hours (+/- 2 hours) for 7 days. It is acceptable for the timing of the first 2 doses to be modified in order to accommodate subsequent dosing on a Q12 hour schedule that meets institution's standard of care procedures. *Study drug infusions should not begin if the subject's mean arterial pressure (MAP) is less than 65 mmHg.*

 Collected once during screening/baseline, at Day 7 and Day 14 (while in the hospital); blood sample to be stored on site for analysis by central lab at end of study

 IL-1 beta, IL-6, TNF-alpha, IL-10

 Screening sample to be performed by local lab with a duplicate sample collected for central lab analysis. Subsequent samples collected at Day 7 and Day 14 (while in the hospital) for central lab analysis. Nasopharyngeal sample required unless subject is intubated, in which case pulmonary secretion collected.

 If viral load test has been performed within 7 days of baseline, no repeat is necessary at baseline

 Collected pre and post first infusion on Day 1 and Day 3 for central lab analysis

 Adverse Events will be assessed weekly after hospital discharge, for a total of 6 weeks from Day 1 and encompassing at least 30 days after end of GC4419/placebo dosing. Post-treatment AE assessments may be done on an outpatient basis for subjects who are discharged from the hospital.

 As Clinically Indicated, Record Worst Value for Any Day When Multiple Labs are Drawn.

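### Appendix 2 scores the kidney by serum creatinine alone, so dialysis or CRRT can turn some days of renal failure into days with SOFA 6 or less

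*Combined protocol and SAP*

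**What the plan says.** Appendix 2 prints six SOFA items of 0-4 points each. The renal row is "Creatinine, mg/dL", with classes below 1.2 (0 points), 1.2-1.9 (1), 2.0-3.4 (2), 3.5-4.9 (3) and above 5 (4). It has no urine-output criterion and no line for dialysis or CRRT. The appendix introduces the score as one that "is used to assess a patient's mortality risk".

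Section 11.5.2 lists "days alive with a SOFA score of 6 or less" among nine secondary endpoints. Section 5.2 sets the window: "The following secondary objectives will be assessed through a 28-day period to align with the primary objective". The Synopsis limits SOFA to the ICU. In Appendix 1, the SOFA footnote reads "Record worst value once a day assessed 8am-6pm" and the laboratory footnote "Record Worst Value for Any Day When Multiple Labs are Drawn".

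RRT on study is expected. The Synopsis (dosing rationale) keeps dialysis sessions apart from infusions and adds "If continuous renal replacement therapy is required for >24 hours, dosing with blinded GC4419/placebo will be discontinued". Both statements concern dosing; neither concerns scoring. Section 7.2 excludes stage IV chronic kidney disease and maintenance hemodialysis, so RRT on study would usually be newly started. Section 9.2 foresees creatinine above 5 mg/dL, the 4-point class. Appendix 1 has no row for RRT status.

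**The concern.** Dialysis and CRRT remove creatinine from the blood whether or not the kidneys recover. If the printed scale is applied literally, a subject can gain a better renal score because organ support was started. A score meant to track mortality risk should not behave that way, and the endpoint can credit such a day as a good one.

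Section 4.1.3 notes that "renal failure does seem to be a substantial issue" and argues that this drug class reduces kidney injury, so RRT use could plausibly differ by arm. If the drug protected the kidney, the placebo arm would have more RRT days and collect more wrongly credited days, so the benefit would be understated. If the drug harmed the kidney, the error on this endpoint would favour the drug. Because Appendix 1 does not record RRT by day, the problem may not be reliably correctable at analysis.

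**Working it through.** **1. Is the printed table complete?** Six items x 4 points = 24, which matches the printed total of 0-24. No separate renal row has been lost, so creatinine is the only renal input.

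**2. When does a day change status?** Let N be the sum of the five non-renal items (0-20), a the renal points without RRT, and b the renal points with creatinine lowered by RRT. The day moves from above 6 to 6 or less when N + a > 6 and N + b <= 6, that is, when 7 - a <= N <= 6 - b.

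| Renal points without RRT | On RRT | Creatinine reached (mg/dL) | Non-renal sums that change status |
|---|---|---|---|
| 4 | 0 | below 1.2 | 3-6 |
| 4 | 1 | 1.2-1.9 | 3-5 |
| 4 | 2 | 2.0-3.4 | 3-4 |
| 4 | 3 | 3.5-4.9 | 3 |
| 3 | 0 / 1 / 2 | as above | 4-6 / 4-5 / 4 |

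From class 4, a day with N of 0-2 already counted as a success, and a day with N of 7 or more never counts.

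**3. Two constructed records scored by Appendix 2.**
- Record A: PaO2/FiO2 180 (3), platelets 120 (1), bilirubin 1.0 (0), MAP 75 without vasopressor (0), Glasgow Coma Scale 14 (1), so N = 5. With creatinine 5.4 (4) the total is 9, not counted. With creatinine 1.6 on CRRT (1) it is 6, counted.
- Record B: PaO2/FiO2 250 (2), platelets 200 (0), bilirubin 0.9 (0), MAP 68 (1), Glasgow Coma Scale 15 (0), so N = 3. With creatinine 5.2 (4) the total is 7, not counted. With creatinine 2.4 on CRRT (2) it is 5, counted.

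**4. How far might creatinine fall?** The documents give no figure. Assume generation of 10-20 mg/kg/day, CRRT clearance of 20-30 mL/kg/h (4.8-7.2 dL/kg/day) and no residual kidney function. Steady state = generation / clearance, from 10 / 7.2 = 1.4 to 20 / 4.8 = 4.2 mg/dL. These values score 1 to 3, an error of 3 to 1 points from class 4. The full 4 points needs creatinine below 1.2.

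**5. Who falls in the window?** Take an intubated subject scored literally as having no verbal response. The Glasgow Coma Scale is at most 4 + 1 + 6 = 11 (2 points). PaO2/FiO2 below 300 adds at least 2, and norepinephrine or epinephrine at least 3, so N >= 7 and the day cannot change. Without vasopressors and with PaO2/FiO2 of 100-199, N >= 2 + 3 = 5, so creatinine must fall below 2.0. Subjects on non-invasive ventilation, or weaning, are likelier to lie in the window.

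**6. Scale in the comparison, by assumption only.** Shift in an arm's mean = (share on RRT) x (RRT days per subject) x (share of those days in the window). With an assumed 10 days and 30-60% in the window, that is 3-6 days per RRT subject. RRT use of 20% against 10% gives a between-arm difference of 0.1 x 3 to 0.1 x 6 = 0.3-0.6 days. Equal use, with similar non-renal scores, gives about zero. None of these inputs comes from the documents.

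**The case against.** A reader might infer that starting RRT always lowers the score and makes renal-failure days successes. The documents do not support that: from class 4 the change needs a non-renal sum of 3-6, often less, and step 5 shows that many of the sickest subjects lie outside it. Both constructed records have near-normal consciousness and no vasopressor, so they are possible but selected. This part of the objection stands, except that it weakens if sites impute the verbal score in intubated subjects, which the documents do not address.

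The worst-value rule also helps. A pre-dialysis sample drawn the same day keeps the higher creatinine. Under sustained CRRT, creatinine is low all day and the rule gives little protection. Its reach is also unclear, because the SOFA footnote is limited to 8am-6pm and the laboratory footnote is not.

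A reader might further infer that renal harm would pass as benefit in the trial as a whole. It would not. Adverse-event and laboratory summaries (Section 11.6) would still show it, and this is one secondary endpoint analysed descriptively (Section 11.7.2).

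Finally, Section 11.1 defers technical detail to a separate statistical analysis plan whose text was not available here and may contain a rule. That limits the claim to the text at hand. It does not change the fact that the printed scale, applied as written, gives the wrong answer on such days.

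**Conclusion.** The point holds in conditional form. With creatinine as the sole renal item and no scoring rule for RRT days, RRT can lower SOFA by 1 to 4 points and turn some days into SOFA 6 or less days. From class 4 this occurs only at non-renal sums of 3-6, 3-5, 3-4 or 3, according to the creatinine reached. It rests on one premise from outside the text, that RRT lowers creatinine without renal recovery.

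The number of affected days cannot be calculated, since the documents give neither an RRT rate nor the distribution of non-renal scores. The figures in step 6 are an illustration, and a shift in one arm's mean is not a bias. The comparison is distorted only if RRT use differs by arm. The primary mortality analysis and its power are untouched. The change is worth making because it is cheap and the rule as printed misclassifies, not because a trial conclusion depends on it.

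**What to change.** Add a daily field for renal replacement therapy, yes or no, to Appendix 1 for every day on which SOFA is scored through Day 28. In Appendix 2 or the statistical analysis plan, prespecify that the renal component is 4 on any day with dialysis or CRRT, and keep creatinine-only scoring as a sensitivity analysis. An RRT day then counts as SOFA 6 or less only when the non-renal sum is 0-2.

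The cost is one CRF field and one line of text, with no new procedure or sample. The Synopsis rule on dialysis timing makes sites track RRT around infusions, but dosing lasts 7 days and the endpoint 28, so later days need the field in its own right. The rule overscores somewhat when RRT starts below class 4 or continues after the kidneys recover. Days between intermittent sessions would still be scored by creatinine. This is a scoring rule only and does not change clinical management.

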## APPENDIX 3. GLASOW COMA SCALE SCORE CRITERIA

### Additional Clinical Information regarding SOFA Glasgow Coma Scale Score Criteria

Criteria	Adults	Score	Criteria Score
Best Eye Response (1 – 4)	No eye opening	1	
	Eye opens to painful stimulus	2	
	Eye opens to verbal command	3	
	Eyes open spontaneously	4	
Best Verbal Response (1 – 5)	No verbal response	1	
	Incomprehensible sounds	2	
	Inappropriate words	3	
	Confused	4	
	Oriented	5	
Best Motor Response (1 – 6)	No motor response	1	
	Extension to painful stimulus	2	
	Flexion to painful stimulus	3	
	Withdraws from painful stimulus	4	
	Localizes to painful stimulus	5	
	Obeys commands	6	
Total Score (add three subscores, range from 3 to 15):			

## APPENDIX 4. EXAMPLES OF CYP2D6-SUBSTRATE DRUGS

Red: CYP2D6 substrates commonly prescribed in ICU setting (Zhuo et al *Pharmogenomics of Medications Commonly Used in the Intensive Care Unit*. *Frontiers in Pharmacol*, 2018; 9: 1436.)

**Bold:** Sensitive index substrates that demonstrate an increase in AUC of  $\geq 5$ -fold with strong CYP2D6 inhibitors in clinical DDI studies.
